9.2.1.1 Consultation with Medical Monitor and local hepatologist

Potential drug-induced liver injury events require notification of the Medical Monitor within 24h (eg, by laboratory alert), and the study participant must be discussed with the Medical Monitor as soon as possible. If required, the study participant must also be discussed with the local hepatologist. The local hepatologist is the expert usually consulted by the treating physician for assessment and management of potential hepatic disease. This would usually be a hepatologist, but may be a gastroenterologist. If determined necessary, this discussion should be followed by a full hepatology assessment (see Section 9.2.1.3) and SAE report (if applicable).

9.2.1.2 Immediate action: determination of IMP discontinuation

All PDILI events require immediate action, testing, and monitoring.

The immediate action is dependent on the laboratory values and symptoms of hepatitis or hypersensitivity and ranges from continuation of IMP (followed by immediate investigation) to immediate and permanent discontinuation (see Section 6.4.1 and Table 9-6 for details).

When IMP is discontinued, all concomitant medications and herbal supplements that are not medically necessary should also be discontinued. The investigator should also consider dose reduction for medically necessary concomitant medication and consider changing any medically required concomitant medication known to be hepatotoxic to a suitable alternative.

9.2.1.2.1 IMP restart/rechallenge (if applicable)

Rechallenge with a substance potentially causing drug-induced liver injury is dangerous, may be fatal, and must not occur.

Study participants who are immediately discontinued from IMP due to having met certain criteria for PDILI (as described in Section 6.4.1 and Table 9-6), but for whom an alternative diagnosis is confirmed, can rarely restart IMP. Rechallenge with IMP can occur only if ALL of the following requirements are met:

- The results of additional testing and monitoring described in Section 9.2.1.3 and Section 9.2.1.4 confirm a nondrug-related cause for the abnormal hepatic laboratory parameters and any associated symptoms (ie, a subsequent alternative diagnosis fully explains the hepatic findings).
- No alternative treatment options are available to the study participant.
- The study participant has shown clear therapeutic benefit from the IMP.
- Study participant's ALT or AST elevations do not exceed $\geq 3\times$ ULN.
- Study participant's total bilirubin is $< 1.5\times$ ULN.
- Study participant has no signs or symptoms of hypersensitivity.
- The rechallenge is approved by the UCB responsible physician, DMC, and a hepatologist. The hepatologist must be external to UCB but may be a member of the DMC. It is recommended that the hepatologist be a local hepatology expert or the hepatologist treating the study participant.
- Study participant agrees to the investigator-recommended monitoring plan.

9.2.1.3 Testing: identification/exclusion of alternative etiology

The measurements and additional information required for the assessment of PDILI events when there is a reasonable possibility that they may have been caused by the IMP are detailed in **Table 9-7** (laboratory measurements) and **Table 9-8** (additional information). Results of the laboratory measurements and information collected are to be submitted to the sponsor on the corresponding eCRF. If the medical history of the study participant indicates a requirement for other assessments not included below, these additional assessments should be completed and submitted, as applicable.

All blood samples should be stored, if possible. If tests are done locally for more rapid results, a concurrent sample must also be sent to the central laboratory.

PUBLIC COPY
This document cannot be used to support any marketing application and any extensions or variations thereof.

The following measurements are to be assessed:

Table 9-7: PDILI laboratory measurements

Virology-related	Hepatitis A IgM antibody
	HBsAg
	Hepatitis E IgM antibody
	HBcAb-IgM
	Hepatitis C RNA
	Cytomegalovirus IgM antibody
Immunology	Epstein-Barr viral capsid antigen IgM antibody (if unavailable, obtain heterophile antibody or monospot testing)
	Anti-nuclear antibody (qualitative and quantitative)
	Anti-smooth muscle antibody (qualitative and quantitative)
Hematology	Eosinophil count
Urinalysis	Toxicology screen
Chemistry	Amylase
	If total bilirubin $\geq 1.5 \times$ ULN, obtain fractionated bilirubin to obtain % direct bilirubin
	Serum CPK and LDH to evaluate possible muscle injury causing transaminase elevation
Additional	Prothrombin time/INR ^a
	Serum pregnancy test
	PK sample

ALT=alanine aminotransferase; CPK=creatine phosphokinase; HBcAb-IgM=hepatitis B core antibody-IgM; HBsAg=hepatitis B surface antigen; IgM=immunoglobulin M; INR=international normalized ratio; LDH=lactate dehydrogenase; PDILI=potential drug-induced liver injury; PK=pharmacokinetic; RNA=ribonucleic acid; ULN=upper limit of normal

^a Measured only for study participants with ALT $>8 \times$ ULN, elevations in total bilirubin, and symptoms of hepatitis or hypersensitivity. Hepatitis symptoms include fatigue, nausea, vomiting, and right upper quadrant pain or tenderness; hypersensitivity symptoms include eosinophilia ($>5\%$), rash, and fever (without clear alternative cause).

The following additional information is to be collected:

Table 9-8: PDILI information to be collected

New or updated information
Concomitant prescription and over-the-counter medications (eg, acetaminophen, herbal remedies, vitamins); dosages and dates should be included.
Pertinent medical history, including the following: 
History of liver disease (eg, autoimmune hepatitis, nonalcoholic steatohepatitis or other “fatty liver disease”)Adverse reactions to drugsAllergiesRelevant family history or inheritable disorders (eg, Gilbert’s syndrome, alpha-1 antitrypsin deficiency)Recent travelProgression of malignancy involving the liver (Note: Metastatic disease to the liver, by itself, should not be used as an explanation for significant AST and/or ALT elevations.)
The appearance or worsening of clinical symptoms of hepatitis or hypersensitivity (eg, fatigue, nausea, vomiting, right upper quadrant pain or tenderness, decreased appetite, abdominal pain, jaundice, fever, or rash)
Recent clinically significant hypotension or hypoxemia with compromised cardiopulmonary function
Alcohol and illicit drug use
Results of liver imaging or liver biopsy, if done
Results of any specialist or hepatology consult, if done
Any postmortem/pathology reports

ALT=alanine aminotransferase; AST=aspartate aminotransferase; PDILI=potential drug-induced liver injury

9.2.1.4 Follow-up evaluation

Potential drug-induced liver injury events require follow-up monitoring as described in [Table 9-6](#). Monitoring should continue until liver chemistry values normalize, stabilize, or return to Baseline. Determination of stabilization is at the discretion of the investigator in consultation with the hepatologist (as applicable) and UCB responsible physician, as needed.

9.3 Other safety measurements

9.3.1 Pregnancy testing

Pregnancy testing will consist of serum testing at the Screening Visit (only for study participants with a gap period between the parent study and entry in CIDP04) and Baseline, if serum pregnancy test is not older than 5 weeks prior to entry into CIDP04. Pregnancy testing will consist of urine testing at dosing visits during the Treatment Period and each visit during the Observation Period as indicated in the schedule of study assessments ([Table 5-1](#)). The Screening Visit serum pregnancy testing results must be negative and should be confirmed by a negative urine pregnancy test prior to first dose of IMP. The urine pregnancy test will be performed

locally. A negative urine pregnancy test result should be obtained prior to each dose of IMP. A positive urine pregnancy test must be confirmed using a serum pregnancy test. Pregnancy tests should be administered to all female study participants of childbearing potential, regardless of their use of birth control.

9.3.2 Vital signs

Vital signs will be measured at all visits as indicated in the schedule of study assessments ([Table 5-1](#)).

Vital signs to be assessed are as follows:

- Pulse rate (PR)
- Systolic/diastolic blood pressure (BP)
- Temperature (oral preferred, ear or axillary allowed)

Study participants should be sitting for 5 minutes prior and during the collection of BP and PR measurements. During site Visits 2, 3, and 4, vital signs will be measured prior to IMP administration, at the end of the infusion, and 2 and 4h after the end of the infusion. From Visit 5 to Visit 25, vital signs will be measured predose, at the end of the infusion and 2h after the end of the infusion only. During Treatment Period Part 2, vital signs will be measured predose, and at the end of the infusion. At nondosing visits, vital signs need only be taken once during the visit.

For study participants requiring additional assessments due to AEs (see [Table 5-2](#)), additional vital signs measurements may be taken based on the timing of the assessments.

9.3.3 Physical examination

9.3.3.1 Full physical examination

A physical examination will be performed at the visits specified in the schedule of study assessments ([Table 5-1](#)) and findings will be recorded in the eCRF. A full physical examination will be performed at Screening or Baseline, and the FV (Visit 29). At all other visits (where physical examination is performed), an abbreviated (brief) physical examination will be conducted.

Clinically important abnormal changes in subsequent physical examinations will be recorded as AEs. Physical examinations must be documented in source documentation.

The following body systems will be examined as a part of the complete physical examination: (1) General appearance; (2) Ear, nose, and throat; (3) Eyes; (4) Hair and skin; (5) Respiratory; (6) Cardiovascular; (7) Musculoskeletal; (9) Gastrointestinal; (10) Hepatic; (11) Neurological examination (see also Section [9.3.4](#)); and (12) Mental status.

9.3.3.2 Brief physical examination

The following body systems will be examined at the visits specified in the schedule of study assessments ([Table 5-1](#)) and findings will be recorded in the eCRF. The following body systems will be examined as a part of the brief physical examination: (1) General appearance; (2) Ear, nose, and throat; (3) Eyes; (4) Skin; (5) Respiratory; (6) Gastrointestinal; and (7) Neurological (focused assessment of sensitivity and power).

9.3.4 Neurological examination

In addition to the Screening or Baseline, and FV (Visit 29), a full neurological examination should be performed for any study participant who experiences severe headache (see Section 9.1.10 and Table 5-2). A full neurological assessment will include: (1) General appearance, including posture, motor activity and meningeal signs and, if indicated, following assessments to be done; (2) Cranial nerves examination; (3) Motor system examination, including muscle tone and power and sensory system examination – light touch; (4) Reflexes, including deep tendon reflexes; (5) Coordination, gait (if possible); and (6) Fundoscopy.

A brief neurological assessment will include a selected assessment of the following: cognition, general, reflexes, muscle strength, and coordination/cerebellar function.

9.3.5 12-lead ECG

A standard 12-lead ECG will be performed at the visits specified in the schedule of study assessments (Table 5-1). Care should be taken to assure proper lead placement and quality ECG recordings. Study participants should rest in a supine position in a controlled, calm environment for at least 15 minutes prior to the recording and should be motionless during the recording. The ECG will be performed in triplicate prior to blood collection for assessment of laboratory parameters.

The ECGs will be read at a central site. The PR, RR, QRS, QT, and corrected QT (QTc) intervals and heart rate will be recorded. All ECG readings from an individual study participant should be read by the same reader, if possible. Findings will be recorded in the eCRF.

For the QTc, the following correction formula will be applied:

$$\text{Fridericia's correction: } QTc = QT/RR^{0.33}$$

9.3.6 Assessment and management of TB and TB risk factors

With the currently available data, TB is not considered as an important potential or identified risk for treatment with rozanolixizumab. As immunomodulation may carry risk of new or activation of LTBI, UCB has conservatively developed TB detection and management procedures taking into account the most current recommendations of international guidelines (2010 WHO) and most recent literature, covering any infection by the mycobacteria TB complex.

Appropriate rigorous precautions are being taken within this protocol to monitor the risk of TB infection in this study (see Section 6.2.1 Exclusion Criterion 20 and Section 6.4 Withdrawal Criteria). The following are the key considerations of these procedures:

TB tests at Screening

The IGRA and Tuberculosis Questionnaire are required as indicated in schedule of assessments (Table 5-1).

- TB screening is mandatory both before study entry and during the conduct of the study. The preferred screening test is the IGRA performed at a central laboratory.
 - The IGRA result must be negative for study participants to enroll in this study.

- Study participants who test positive for IGRA test should be excluded from the study and referred for appropriate medical evaluation according to the local medical practice guidelines.
- If the result of the IGRA test is indeterminate, the particular IGRA test previously performed may be repeated once; if positive or indeterminate on retest, the study participant may not be treated with study drug and, if already enrolled, must undergo appropriate study specified withdrawal procedures. The retest must be done during the protocol-defined Screening window.
- In addition to IGRA test, study participants will be evaluated for signs and symptoms of latent or active TB infection and for risk factors of exposure to TB, using the TB Questionnaire, at Screening. Study participants with known TB, at a high risk of acquiring TB or with LTBI should be excluded from this study as described in Exclusion Criteria (Section 6.2.1). For study participants directly enrolling in CIDP04, no new TB assessment will be performed and values of TB assessment performed at Visit 17 and/or FV (Visit 21) of CIDP01 will be used.

Monitoring for TB during the study

Study participants will be monitored for signs/symptoms of TB using routine pharmacovigilance measures for AEs. Study participants reporting AEs related to signs/symptoms of TB will be evaluated for LTB and active TB according to the local medical practice guidelines.

Study participants with confirmed LTB or active TB or NTMB infection will be immediately withdrawn from the study as described in Section 6.4 Withdrawal Criteria. Confirmed LTB, active TB, and NTMB must be reported to the Sponsor immediately regardless of seriousness using the SAE data collection tool. Additional information received by the investigator should be provided to the Sponsor within 24 hours of awareness.

Once withdrawn from study treatment, study participants should return for the POET, complete all early withdrawal assessments, and complete the follow-up visits.

TB tests at Final Visit

Study participants will be evaluated for signs and symptoms of latent or active TB infection and for risk factors of exposure to TB, using the Tuberculosis Questionnaire, at the Final /PEOT Visit. See the ‘Tuberculosis Signs and Symptoms Questionnaire’ section for further instructions on using the questionnaire.

Signs and symptoms of TB

The investigator should consider all potential sites of infection when assessing for TB during the physical examination, and other evaluations, and based on the study participant’s history.

Common symptoms with which the study participant may present with include cough, blood in sputum, night sweats, lymphadenitis, joint pain/swelling, spinal deformity, headache/confusion, abdominal pain mimicking inflammatory bowel disease, frequent or painful urination, scrotal mass in men and pelvic inflammatory disease in women as well as other symptoms, or nonspecific symptoms. This is not an exhaustive list and unusual presentations should always be considered.

TB Signs and Symptoms Questionnaire

The questionnaire “Evaluation of signs and symptoms of tuberculosis” should be used as a source document. The questionnaire will assist with the identification of study participants who may require therapy for TB. A study participant who answers “Yes” to the question “[REDACTED]

[REDACTED] at Screening is excluded. A “Yes” response to any of the other questions within the questionnaire at Screening should trigger further careful assessment to determine if study participant has latent or active TB. A “Yes” response to any of the questions at the end of the study should trigger further assessments as per local medical guidelines to determine if the study participant has either LTB or active TB infection.

LTB infection, active TB or other NTBM identified during study

During the study, study participants who develop evidence of LTB infection or active TB or NMTB must immediately stop further administration of study drug and will be referred to an appropriate medical specialist for further evaluation.

Confirmed LTB or active TB or NTMB must be reported to the Sponsor immediately as described above.

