of Part 2). The Observation Period will not be performed in the event of a study participant continuing treatment with rozanolixizumab after the end of the study (ie, in case of an Access Program), in which case only the PEOT (Visit 26) Visit will be performed.

During the Treatment Periods (Part 1 and Part 2), study participants will have weekly visits (either on site or at home) during which they will be dosed with an sc infusion of rozanolixizumab up to [REDACTED]. The initial dose in the study will be based on the dose the study participant has received at the completion of the parent study (eg, CIDP01). For study participants who were known to be on placebo in the parent study, a starting dose of [REDACTED] will be used. The maximum dose will be [REDACTED]. See Section 7.2 for details on treatment to be administered.

During the first 4 weeks of the Treatment Period (Part 1), all visits will be on site. During Weeks 5 to 8, home visits and on-site visits will be alternating (Weeks 5 and 7 will be on site; Weeks 6 and 8 will be at home). Starting at Week 9 and through the end of the Treatment Period (Week 24 and if applicable, Week 76), study participants will have 1 visit on site followed by 3 visits at home for every 4-week period.

After the completion of the Treatment Period(s) (starting at Week 25 for study participants only completing Part 1 or from Week 77 for study participants completing both Part 1 and Part 2 or at any early timepoint in case of PEOT), study participants will enter the 8-week Observation Period where no IMP will be administered. During the Observation Period, study participants will have on-site visits at the entry and exit of the Observation Period (Weeks 25/77, and 32/84, and home visits at Weeks 27/79 and 29/81). Study participants can return to their SOC during the Observation Period. In case the study participant enters an Access Program, no Observation Period will be performed with the exception of the PEOT (Visit 26) Visit which will be immediately completed.

At the discretion of the investigator and/or study participant, home visits can be changed to site visits (eg, for safety reasons). In case an on-site visit cannot be performed, the next visit will be performed at site instead of at home, and all safety assessments that should have been completed at the missed visits will be performed.

The assessments to be completed during each visit are presented in Table 5-1.

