			2 BL	3	4	5	6	7	8	9	10 14 18 22	11 15 19 23	12 16 20 24	13 17 21 25	Additional Visits numbered sequentially	26 PEOT	27	28	29 FV	
	Week	-5 to -2	1	2	3	4	5	6	7	8	9	10 13 17 21	11 14 18 22	12 15 19 23	Every 4 weeks	Weekly in between site visits	25 or 77	27 or 79	29 or 81	32 or 84
Full neurological examination ¹		X	X ^f																	X
Brief neurological examination				X	X	X	X		X		X		X			X		X		
12-lead ECG		X	X ^f	X	X	X			X		X		X		X ^m		X			X
Labs (hematology, chemistry, urinalysis)		X	X ^f	X	X	X			X		X		X		X		X			X
Serology for HIV, hepatitis B, and hepatitis C ⁿ		X																		
Serum/urine pregnancy test ^o	X	X ^f	X	X	X	X	X	X	X	X	X	X	X	X		X	X	X	X	
IGRA tuberculosis test ^p	X	X ^f																		X

Table 5-1: Schedule of study assessments

Assessments	Visit	1 Scr ^b	24-Week Treatment Period (Part 1)												52-Week Additional Treatment Period (Part 2 - Optional) ^a		8-Week Observation Period (Optional)			
			2 BL	3	4	5	6	7	8	9	10 14 18 22	11 15 19 23	12 16 20 24	13 17 21 25	Additional Visits numbered sequentially	26 PEOT	27	28	29 FV	
	Week	-5 to -2	1	2	3	4	5	6	7	8	9	10 13 17 21	11 14 18 22	12 15 19 23	Every 4 weeks	Weekly in between site visits	25 or 77	27 or 79	29 or 81	32 or 84
Tuberculosis Signs and Symptoms Questionnaire		X													X ^q	X ^q				X
Contact IRT		X	X	X	X	X	X	X	X	X	X	X	X	X	X	X	X			X
Administration of IMP			X	X	X	X	X	X	X	X	X	X	X	X	X ^r	X ^r				
Blood sampling for PK of rozanolixizumab ^s		X ^f		X				X		X ^t					X ^m		X			
ADA (Anti-rozanolixizumab antibodies)		X ^f		X				X		X ^t					X ^m		X			X
Serum complement (C3, C4) and plasma complement (C3a, C5a) ^u		X	X					X		X					X					

Table 5-1: Schedule of study assessments

Assessments	Visit	1 Scr ^b	24-Week Treatment Period (Part 1)												52-Week Additional Treatment Period (Part 2 - Optional) ^a		8-Week Observation Period (Optional)			
			2 BL	3	4	5	6	7	8	9	10 14 18 22	11 15 19 23	12 16 20 24	13 17 21 25	Additional Visits numbered sequentially	26 PEOT	27	28	29 FV	
	Week	-5 to -2	1	2	3	4	5	6	7	8	9	10 13 17 21	11 14 18 22	12 15 19 23	Every 4 weeks	Weekly in bet- ween site visits	25 or 77	27 or 79	29 or 81	32 or 84
Serum cytokines ^u			X	X					X		X					X				
Vaccination-specific antibody titers (tetanus and influenza Type A)		X							X		X ^v				X ^m		X			
Immunoglobulins (total IgG and IgG subclasses)	X	X ^f	X	X	X	X	X ^w	X	X ^w	X	X ^w	X ^w	X ^w	X ^w	X	X ^w	X			X
NF-L		X ^f							X						X ^x		X ^y			
IgA, IgM, IgE		X ^f	X	X	X	X		X		X				X ^m		X			X	

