^h Body weight is collected every 6 months during Treatment Period Part 2 starting at first visit in this period and will be used to select the correct volume for dose infusion from these timepoints.

ⁱ A full C-SSRS assessment will be performed only when the study participant has a positive response to the suicidal ideation query. If a study participant has active suicidal ideation as confirmed by the answer “Yes” to Question 4 or Question 5 of the C-SSRS assessments, the study participant will be excluded or withdrawn from the study and immediately referred to a Mental Healthcare Professional.

^j Only performed every 24 weeks.

^k Not required for study participants who had a Screening Visit.

^l The full neurological examination includes a fundoscopy. In addition to the FV, a full neurological examination should be performed for any study participant who experiences severe headache (refer to Section 5.2.1 and Table 5-2).

^m Assessment to be performed every 12 weeks (Weeks 25, 37, 49 and 61).

ⁿ Serology includes hepatitis C virus (HCV)-antibodies (Ab)+, hepatitis B virus antibodies (HBsAg and HBcAb), human immunodeficiency virus antibodies (HIV1 and HIV2).

^o In case of immediate entry from the parent study, the serum pregnancy test from the parent study should not be older than 5 weeks prior to entry into this CIDP04 study and the urine pregnancy test done at Visit 2 must both be negative before dosing. In case of gap period between the parent study and entry in CIDP04, a serum test will be performed at Visit 1 (Screening). Pregnancy testing will consist of urine testing at dosing visits during the Treatment Period Part 1, monthly urine testing during Treatment Period Part 2 and at each visit during the Observation Period for women of childbearing potential. A positive urine pregnancy test must be confirmed using a serum pregnancy test. Note that the final urine pregnancy test of the study should be no longer than 90 days after the final dose of IMP.

^p The IGRA test will be performed in a central laboratory.

^q Tuberculosis signs and symptoms Questionnaire must be done at least every 12 weeks.

^r Self-administration may be performed by study participant under the supervision of the home nurse after full training.

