8.2.9 Visits 10, 14, 18, and 22 (Weeks 9, 13, 17, and 21)

The following procedures will be performed at Visits 10, 14, 18, and 22 (Weeks 9, 13, 17, and 21):

- PROs should be conducted in the order specified in Section 10.4:
 - iRODS assessment – to be performed before any other assessment

- CIDP PRO instrument
- Fatigue scale
- PGIS
- PGIC
- Query for suicidality
- Withdrawal criteria assessment
- Prior and concomitant medications
- Concomitant medical procedures
- Vital signs (prior to IMP administration, at the end of the infusion, at 2h after the end of the infusion)
- 12-lead ECG
- Recording of AEs
- Brief physical examination
- Brief neurological examination
- Urine sample for urinalysis and urine pregnancy test
- Blood sample (all samples should be taken predose unless otherwise specified; the laboratory manual will provide guidance on the order of sample collection) for:
 - Clinical laboratory tests (ie, hematology and clinical chemistry)
 - PK of rozanolixizumab (does not apply to Visit 10)
 - ADA (anti-rozanolixizumab antibodies) (does not apply to Visit 10)
 - Serum complement (C3, C4) and plasma complement (C3a, C5a) (predose and 4h postdose)
 - Serum cytokines (predose and 4h postdose)
 - Vaccination-specific antibody titers (tetanus and influenza Type A) (only at Visit 14)
 - Immunoglobulins (total IgG and IgG subclasses)
 - IgA, IgM, IgE
 - CIDP-specific auto-antibodies
 - Exploratory biomarker analysis
- Contact IRT
- Administer IMP
- INCAT assessment
- RT-MRC assessment

- Assessment of grip strength by site personnel

8.2.10 Home Visits 11 to 13, 15 to 17, 19 to 21, and 23 to 25 (Weeks 10 to 12, 14 to 16, 18 to 20, and 22 to 24)

The following procedures will be performed at Visits 11 to 13, 15 to 17, 19 to 21, and 23 to 25 (Weeks 10 to 12, 14 to 16, 18 to 20, and 22 to 24) by a healthcare professional visiting the study participant at his/her home:

- Query for suicidality
- Tuberculosis Signs and Symptoms Questionnaire (only at Visit 13, 17, 21, and 25)
- Withdrawal criteria assessment
- Prior and concomitant medications
- Concomitant medical procedures
- Vital signs (prior to IMP administration, at the end of the infusion, at 2h after the end of the infusion)
- Recording of AEs
- 12-lead ECG (only at Visits 12, 16, 20, and 24)
- Blood sample for clinical laboratory tests (ie, hematology and clinical chemistry) (only at Visits 12, 16, 20, and 24)
- Urine sample for urinalysis (only at Visits 12, 16, 20, and 24)
- Urine pregnancy test

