8.4.1 Visit 26 (Week 25 or Week 77 or PEOT)

The following procedures will be performed at Visit 26 (Week 25 or Week 77 or PEOT):

- PROs should be conducted in the order specified in Section 10.4:
 - iRODS assessment – to be performed before any other assessment
 - Fatigue scale
 - CIDP PRO instrument
 - PGIS
 - PGIC
- Query for suicidality
- Withdrawal criteria assessment
- Prior and concomitant medications
- Concomitant medical procedures
- Vital signs (taken once during the visit)
- Body weight
- 12-lead ECG
- Recording of AEs
- Brief physical examination
- Brief neurological examination
- Urine sample for urinalysis
- Urine pregnancy test for women of childbearing potential
- Blood sample (all samples should be taken predose unless otherwise specified; the laboratory manual will provide guidance on the order of sample collection) for:
 - Clinical laboratory tests (ie, hematology and clinical chemistry)
 - PK of rozanolixizumab
 - ADA (anti-rozanolixizumab antibodies)

- Immunoglobulins (total IgG, IgG subclasses)
- NF-L (Visit 26 [Week 25] only or PEOT only if Treatment Period 1 is performed)
- IgA, IgM, IgE
- CIDP specific auto-antibodies (Visit 26 [Week 25] only or PEOT only if Treatment Period 1 is performed)
- Vaccination-specific antibody titers (tetanus and influenza Type A)
- Contact IRT
- INCAT assessment
- RT-MRC assessment (Visit 26 [Week 25] only)
- Assessment of grip strength by site personnel

8.4.2 Visits 27 and 28 (Weeks 27 and 29, and at 79 and 81), Home Visits

The following procedures will be performed at Visits 27 and 28 (Weeks 27 and 29, and at 79 and 81) by a healthcare professional visiting the study participant at his/her home:

- Query for suicidality
- Withdrawal criteria assessment
- Prior and concomitant medications
- Concomitant medical procedures
- Vital signs (taken once during the visit)
- Recording of AEs
- Urine pregnancy test

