8.5 Premature end of treatment and Final Visit

All study participants who withdraw early from the Treatment Period should attend a PEOT Visit, which will be scheduled as close as possible to the date of the decision for the study or treatment withdrawal.

Study participants are encouraged to complete all visits of the Observation Period following the PEOT Visit by either coming to the clinic or as home nursing visits, if appropriate.

In case a study participant is not willing to attend the visits in the Observation Period, the study participant should still be strongly encouraged to attend at least the PEOT Visit and the FV.

The FV should be scheduled 8 weeks after their final dose of IMP.

The assessments to be done at the PEOT Visit and the FV are the same as those at Visit 26 and Visit 29, respectively.

A study participant entering the Access Program after completion of part or full Treatment Period 2 without any relapse will not complete the Observation Period but will only perform the PEOT/V26 one week after the last IMP dispensing for the study.

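### Protocol 9.3.6 requires the TB questionnaire at the Final/PEOT Visit, but the Visit 26/PEOT list in 8.4.1 and the Visit 26/PEOT column of Table 5-1 leave it out

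*Protocol*

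**What the plan says.** Protocol 9.3.6, in its paragraph on TB tests at the Final Visit, requires evaluation for signs, symptoms and exposure risk "using the Tuberculosis Questionnaire, at the Final /PEOT Visit". It attaches an action: a positive "response to any of the questions at the end of the study should trigger further assessments" for latent or active infection.

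Section 8.4.1 gives the procedures for Visit 26, whether it falls at Week 25, at Week 77 or as a PEOT visit. The questionnaire is not among them. Section 8.5 links the lists: "The assessments to be done at the PEOT Visit and the FV are the same as those at Visit 26 and Visit 29, respectively".

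Other visit lists name the questionnaire where it is wanted. The Part 1 home visits (8.2.10) have "Tuberculosis Signs and Symptoms Questionnaire (only at Visit 13, 17, 21, and 25"), the Part 2 site visits (8.3.1) have it every 12 weeks, and Visit 29/FV (8.4.3) includes it. Footnote q of Table 5-1 adds: "Tuberculosis signs and symptoms Questionnaire must be done at least every 12 weeks".

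For a participant who continues rozanolixizumab through an Access Program, section 5.1 drops the Observation Period, "in which case only the PEOT (Visit 26) Visit will be performed".

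**The concern.** One section of the protocol requires a safety check at a visit, and the operative list for that visit omits it. Sites usually work from the visit list and the schedule, so the check is likely to be missed.

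If the Final Visit follows, the omission does little harm, because the questionnaire is done there. The exposed participants are those for whom Visit 26/PEOT is the end of the study. They leave without the exit questionnaire that 9.3.6 requires, so the follow-up rule for a positive answer cannot operate. Access Program entrants also go on receiving the drug.

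**Working it through.** **Step 1. The instructions side by side (current protocol text, not the amendment log).**

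| Place | What it provides | Questionnaire at Visit 26/PEOT? |
|---|---|---|
| 9.3.6 | Questionnaire at the Final/PEOT Visit | Required |
| 8.4.1 | Visit 26/PEOT procedure list | Not listed |
| 8.5 | PEOT assessments are those of Visit 26; FV assessments are those of Visit 29 | Carries over the omission |
| 8.4.3 | Visit 29/FV list includes it | Not applicable |
| Table 5-1, row "Tuberculosis Signs and Symptoms Questionnaire" | Marks at Screening, two treatment-period columns (footnote q) and Visit 29 | Blank |
| Table 5-1, footnote q | Maximum interval between questionnaires | Silent on exit |

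The table reading comes from extracted text. The body-weight and Contact IRT rows split into the same number of cells as the questionnaire row, and both carry a Visit 26 mark where the questionnaire row has none. The two footnote-q marks may have moved one column in extraction. Sections 8.2.10 and 8.3.1 suggest that they belong under Visits 13/17/21/25 and the Part 2 site visits. Neither alignment puts a mark under Visit 26. Section 8.4.1 is plain text and shows the omission without the table.

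**Step 2. Who has Visit 26/PEOT as the last visit.**

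- Access Program entrants. Sections 5.1, 8.4 and 8.5 give them Visit 26/PEOT and no Observation Period. Section 8.5 places this after part or all of Part 2.
- Early stoppers who do not attend the Final Visit. Section 8.5 foresees participants unwilling to attend the Observation Period and strongly encourages at least the PEOT Visit and the FV. Early stopping is to be expected, because section 6.4 requires permanent discontinuation of IMP on relapse or rescue.

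**Step 3. Age of the last questionnaire at Visit 26/PEOT.** Visit windows are ignored.

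- *Part 1 completer.* Visits 13, 17, 21 and 25 are Weeks 12, 16, 20 and 24. At Week 25 the age is 25 − 24 = 1 week.
- *Part 1 stopper after Week 12.* Questionnaires are 4 weeks apart (16 − 12 = 4), so the age is up to about 4 weeks.
- *Full Part 2 completer, Week 77.* The protocol does not say from which week the 12-week cycle runs, so both readings are shown. From Week 24 the sequence is 24, 36, 48, 60, 72, and 77 − 72 = 5 weeks. From Week 25 it is 25, 37, 49, 61, 73, and 77 − 73 = 4 weeks.
- *Exit part-way through Part 2.* The age is anything up to the interval, so it approaches 12 weeks.
- *Direct entrant stopping before Week 12.* Section 9.3.6 gives no new TB assessment at entry and uses the CIDP01 values. If the CIDP01 questionnaire was done at Visit 17, which is the day of entry (Week 1), then at Week 11 it is 11 − 1 = 10 weeks old.
- *Gap entrant stopping before Week 12.* The only questionnaire is at Screening, 2 to 5 weeks before Visit 2. At Week 11 it is 10 + 2 = 12 to 10 + 5 = 15 weeks old.

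In the last two cases, a participant who received placebo in CIDP01 and skips the Final Visit would complete no questionnaire after first exposure to rozanolixizumab.

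**The case against.** The strongest reply is that 9.3.6 asks for one end-of-participation questionnaire. Its paragraph is headed for the Final Visit, the action rule speaks of the end of the study, and 8.4.3 supplies the questionnaire at the FV. Section 8.4 expects everyone not entering an Access Program to attend the FV, so for an early stopper a missed questionnaire is non-attendance, not a fault in the schedule. This narrows the problem but does not remove it. Access Program entrants have no FV by design. For stoppers who skip the FV, Visit 26/PEOT is the only remaining chance to collect the questionnaire, and 9.3.6 names that visit.

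A second reply is that other safeguards suffice. Section 9.3.6 still instructs sites, footnote q limits the interval, adverse events suggestive of TB are evaluated, and Visit 26 keeps AE recording and a brief physical examination that covers the respiratory system. The protocol does not regard TB as an important risk of this drug. All of this stands and keeps the point minor. But a maximum interval is not an exit assessment, and these safeguards do not settle which of two conflicting instructions a site should follow.

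Third, some of the ages in the working are ceilings, and the direct-entrant figure depends on the CIDP01 schedule, which the documents do not give. That is correct. The inconsistency itself does not depend on any of them.

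**Conclusion.** The concern holds. Section 9.3.6 and the Visit 26/PEOT list cannot both be followed as written, and Table 5-1 sides with the list.

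The practical effect is limited to participants whose last visit is Visit 26/PEOT. The documents do not allow their number to be estimated. It is smallest for Part 1 completers and largest for those leaving part-way through Part 2 or stopping before Week 12. These sizes rest on the scheduled visit weeks, on either of the two starting points for the 12-week cycle and, for direct entrants, on a CIDP01 questionnaire at Visit 17.

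The questionnaire is a listed safety variable, and SAP 10.4.4 provides a listing only. No estimate or summary table changes. This is a minor inconsistency in safety instructions, worth correcting because it is cheap to correct.

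**What to change.** Add the questionnaire to the Visit 26/PEOT list in 8.4.1 and mark the Visit 26/PEOT cell of its row in Table 5-1. The minimum version is conditional: required when Visit 26/PEOT is the participant's last visit, either because of Access Program entry or because the participant will not attend the Final Visit. An unconditional entry is simpler for sites.

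If the sponsor meant the Final Visit only, 9.3.6 should be reworded instead. That choice would leave Access Program entrants with no exit questionnaire and should then be stated openly.

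The cost is one line of text, one table cell and one short questionnaire at an existing site visit. The SAP needs no change, since the results would enter the existing listing.
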